#### Notification to Regulatory Authorities / Gene Therapy Bodies / Ethics Committee

Transgene or its representative will be responsible for reporting of SUSAR and any other SAEs to Regulatory Authorities, IEC(s) / IRB(s) and Gene Therapy Bodies as per local regulation. In case of a SUSAR, Transgene or its representative will inform all investigators involved in the study that such an event has been reported.

The Investigator is responsible for informing local Ethics Committees, IRB(s) of SUSARs, any other SAEs, and any follow-up information as per local regulations.

Transgene or its representative is responsible for ensuring that all AEs and SAEs that are observed or reported during the study are collected and reported to the FDA in accordance with CFR 312.32 (IND Safety Reports).

#### **8.2.4. Special situations**

##### Overdose

An overdose is defined as the accidental or intentional administration of any dose of a product that is considered both excessive and medically important.

For this study, any dose of IMP greater than the assigned dose, and considered excessive and medically important by the Investigator, will be considered an overdose.

All occurrences of overdose must be reported as SAEs (see Section 8.2.3).

In the event of an overdose, the Investigator or treating physician should:

- Contact the Medical Monitor immediately
- Closely monitor the participant for AEs/SAEs and laboratory abnormalities
- Document the quantity of the excess dose as well as the duration of the overdosing in the eCRF

Decisions regarding dose interruptions or modifications secondary to an overdose will be made by the Investigator in consultation with the Medical Monitor based on the clinical evaluation of the participant.

Any overdose should be reported to Transgene within 24 HOURS and documented and followed-up using an “Overdose form”. In addition, any associated symptoms should be reported as an AE or SAE.

#### Other safety considerations

Any significant worsening noted during interim or final physical examinations, electrocardiogram, CT-scan, any other potential safety assessment required or not required by protocol should also be recorded as a non-serious or serious AE, as appropriate, and reported accordingly.

#### **8.2.5. Laboratory values, vital signs, physical findings and other safety data**

Laboratory tests results will be recorded on the laboratory results forms of the eCRF.

Clinically relevant abnormal laboratory or tests results, clinically relevant abnormal findings in vital signs measurements, physical examinations or ECGs will be reported by the Investigator and followed until normal, stabilization or back to baseline value or until the safety follow-up visit if they are not related to the IMP. If related to the IMP, they should be followed even after the safety follow-up visit (see Section 8.2).

[figure not shown]
Any laboratory result abnormality fulfilling the criteria for a serious adverse event (SAE) should be reported as such, in addition to being recorded as an AE on the eCRF.

Any treatment-emergent abnormal laboratory result which is clinically significant, i.e., meeting one or more of the following conditions, should be recorded as a single diagnosis on the adverse event form in the eCRF:

- accompanied by clinical symptoms
- leading to a change in study medications (e.g., interruption or permanent discontinuation)
- requiring corrective treatment or clinical management

#### **8.2.6. Translational research and exploratory evaluations**

[figure not shown]
[figure not shown]
Mutational load and impact of vaccination on tumor mutational profile; specifically, tumor exome and transcriptome sequencing prior to initiation of treatment will allow identification of tumor specific mutations and their respective level of expression in tumor tissue. **CCI**

CCI

CCI

## 9. STATISTICAL METHODS PLANNED AND SAMPLE SIZE

### 9.1. Data sets analyzed

#### 9.1.1. Screening period

All patients having signed the ICF will be considered as screened patients and included in the screening population (SCR). The percentage of patients not treated afterwards and the corresponding reason, will be analyzed. Available data from screen failed patients will be listed separately and presented according to the statistical plan.

#### 9.1.2. Treatment period

Patients will be enrolled in separate cohorts at the time of treatment initiation according to:

- Cohort A: patients develop an asymptomatic relapse defined on the basis of progressive serial elevations of serum CA-125 (GCIG criteria) or documentation of low volume radiological disease with CA-125 > Upper Limit of Normal (ULN). Low volume radiological disease is defined as radiologically visible disease excluding intra-hepatic or intra-splenic metastases, ascites or pleural effusion thought to require drainage.
- Cohort B: patients develop an asymptomatic relapse with measurable disease excluding intra-hepatic or splenic metastases, ascites or pleural effusion thought to require drainage, whatever serum CA-125 level and for whom further treatment is not planned within 2 months. Longest diameter on CT-scan must not exceed 2 cm for non-nodal lesions and 2.5 cm in the short axis for nodal lesions.

Safety Analysis Set (SAF): all patients included and who received at least one dose of TG4050 will be included in the SAF. This is the primary dataset for safety analyses.

Evaluable Safety Set (ESAF): first 3 patients in SAF who completed the first 6 weeks of treatment or discontinued due to a DLT. Patients who are not evaluable for safety analysis during the run-in phase, or who are withdrawn for other reasons than toxicity, will be replaced.

Evaluable Per-Protocol Set (EPP): all included patients in each cohort without any major protocol deviation who received at least the 6 first weekly injections of TG4050 corresponding to the treatment induction phase and have at least two baseline and two post-baseline evaluations of CA-125 and one baseline and one post-baseline CT-scan or MRI.

Modified Evaluable Per-Protocol (mEPP): patients from EPP in each cohort who are evaluable for immune response meaning at least one pre-dose evaluation and one post-baseline evaluation.

## 9.2. Determination of sample size

No formal sample size calculation is planned.

## 9.3. Study endpoint

### 9.3.1. Primary endpoint

Adverse events will be assessed throughout the treatment period and graded according to NCI CTCAE version 5.

### 9.3.2. Secondary endpoints

- Failure to provide rate: percentage of patients for whom TG4050 cannot be provided and the reason for not being able to provide the vaccine will be recorded.
- Failure to treat rate: percentage of patients who cannot receive TG4050 and the reason that prevent patient from being treated.
- CA-125 doubling time and half-life as appropriate
- Time to normalization of CA-125
- Response according to GCIC criteria
- Time to measurable relapse in Cohort A and Time to progression in Cohort B per RECIST 1.1
- Tumor response according to RECIST 1.1

### 9.3.3. Translational research

The following exploratory endpoints will be investigated:

- CCI
- [REDACTED]
- [REDACTED]
- [REDACTED]
- [REDACTED]
- [REDACTED]
- [REDACTED]

- Quantification of tumor and immune related biomarkers

#### 9.4. Statistical and analytical plans

##### 9.4.1. Safety analyses for the treatment period

All safety analyses will be performed and summarized in the SAF. Safety analyses will also be conducted in each cohort of treated patients.

###### Adverse events

AE summaries will include all TEAEs corresponding to AEs that have started on or after the day of first study treatment administration or that have worsened on or after first TG4050 administration and starting no later than 30 days after the date of last study treatment administration. All AEs, significant AEs, AEs leading to discontinuation of study treatment, severe AEs (Grade 3 or 4) and serious AEs (SAE) will be listed and summarized by System Organ Class (SOC) and Preferred Term (PT), intensity (based on the NCI CTCAE grades, relationship to TG4050).

Written narratives will be produced for all SAEs and unexpected or other significant AEs that are judged to be of special interest because of their clinical importance.

Adverse events/SAEs occurring after signing the Informed Consent Form (ICF) but before starting study treatment, including those observed in patients screened but not included will be listed separately from those occurring after treatment start.

SAEs occurring more than 30 days after administration of the last dose of TG4050 and evaluated by the investigator as related to TG4050 will be listed separately.

###### Fatal Events

All fatal events will be listed and summarized by System Organ Class (SOC) and Preferred Term (PT). The nature of the event leading to death should be recorded. Sudden/unexplained death will be coded as “death”.

Fatal events will be summarized by presenting the number and percentage of patients who died. Data will be presented by SOC and PT using MedDRA coding.

Fatal events occurring after signing the Inform Consent Form (ICF) but before starting study treatment in patients screened but not included will be listed separately from those occurring after treatment start.

###### Laboratory abnormalities

The summaries will include all laboratory assessments collected from baseline assessment until 30 days after treatment discontinuation. All laboratory assessments will be listed and those collected during 30 days after study treatment discontinuation will be flagged in the listings.

All laboratory values will be converted into SI units and will have a severity grade calculated using appropriate common terminology criteria for AEs (NCI-CTCAE, version 5). A listing of laboratory values will be provided by laboratory parameter and patient. A separate listing will display notable laboratory abnormalities (i.e., newly occurring CTCAE Grade 3 or 4 laboratory toxicities). The frequency of these notable laboratory abnormalities will be displayed by parameter. The shift tables using CTCAE grades to compare baseline to the worst post-baseline value will be produced for all relevant safety measures as described in the statistical analysis

plan. Note that for parameters with two directions abnormalities (hypo/hyper), two tables will be presented.

#### Other safety data

Other safety data (e.g., vital signs, electrocardiogram) will be listed, notable values will be flagged, and any other information collected will be listed as appropriate. Any statistical procedures performed in order to explore the data will be used only to highlight any interesting comparisons that may warrant further consideration.

#### **9.4.2. Efficacy analyses for the treatment period**

The analysis of the efficacy endpoints will be performed on the evaluable population (EPP) for efficacy in each cohort of treated patients.

CA-125 doubling time and half-life as appropriate, time to normalization and response according to GCIG as well as time to measurable relapse or progression will be analyzed. Time to measurable relapse in Cohort A and Time to progression in Cohort B per RECIST 1.1 Tumor response according to RECIST 1.1. will be analyzed.

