## **6 DEFINITION OF THE POPULATIONS TO BE ANALYSED**

### **6.1 Populations**

- Screening period:**

All patients having signed the ICF will be considered as screened patients and included in the screening population (SCR). The percentage of patients not treated afterwards and the corresponding reason, will be analyzed.

Screening population (SCR): all patients who have signed the ICF.

- **Treatment period:**

Safety Analysis Set (SAF): all patients who received at least one dose of TG4050 will be included in the SAF. This is the primary dataset for safety analyses.

Evaluable Safety Set (ESAF): first 3 patients who completed the first 6 weeks of treatment or discontinued before due to the occurrence of a DLT. Patients who are not evaluable for safety analysis during the run-in phase or who are withdrawn for other reasons than toxicity, will be replaced.

Evaluable Per-Protocol Set (EPP): all treated patients without any major protocol deviation who received at least 6 injections of TG4050 corresponding to the treatment induction phase.

[figure not shown]
Modified Evaluable Per-Protocol (mEPP): patients from EPP who are evaluable for immune response meaning at least one pre-dose evaluation and one post-dose evaluation.

Given the small number of patients, this population won't be used.

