## 6.2 Major protocol deviations

The identification of major protocol deviations is critical for the EPP definition. A protocol deviation classified as major, will lead to the exclusion of patient from the EPP.

CC1

A non-exhaustive list of protocol deviations including inclusion/exclusion deviations is displayed in APPENDIX 1 – Protocol deviations.

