### **8.3 Analysis of demographic and baseline characteristics**

Analyses will be based on the SAF / EPP populations.

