### 10.2 Listings

Listing number	Title
16.2	PATIENS DATA LISTINGS
16.2.1	Discontinued patients
Listing 16.2.1.1	Screen failure patients and non-inclusion reasons – SCR
Listing 16.2.1.2	Patients' disposition – SAF
16.2.2	Protocol deviation for enrolled patients
Listing 16.2.2.1	Protocol deviations at inclusion for treated patients – SAF
Listing 16.2.2.2	Protocol deviations during study for treated patients – SAF
16.2.4	Demographic data and Baseline characteristics by patient (enrolled patients)
Listing 16.2.4.1.1:2	Demographic and baseline characteristics: SCR/SAF
Listing 16.2.4.2.1:2	History of studied disease – SCR/SAF
Listing 16.2.4.3. 1:2	Prior Anti-Cancer Therapy: Medication – SCR/SAF
Listing 16.2.4.4.1	Relevant Medical History and current Medical Conditions – SAF
Listing 16.2.4.5.1:2	CA-125 concentration at study entry and during screening period – SCR/SAF
Listing 16.2.4.6	Signs and symptoms at baseline – SAF
Listing 16.2.4.7	Serology – SCR/SAF
16.2.5	Compliance and study conduct data
Listing 16.2.5.1	TG4050 administration – SAF
Listing 16.2.5.2	TG4050 administration per patient – SAF
Listing 16.2.5.3	Delayed, cancelled or stopped administration of TG4050 (Listing) – SAF
Listing 16.2.5.4	Discontinuation of study treatment and study (Table) – SAF
Listing 16.2.5.5	Prior and concomitant medications (on or after D1) – SAF
Listing 16.2.5.6	Prior and concomitant medications (before D1) – SAF
Listing 16.2.5.7	Further anti-cancer therapies – SAF
16.2.6	Individual efficacy response data by patient (enrolled patients)
Listing 16.2.6.1	CA-125 concentration during treatment period – SAF
Listing 16.2.6.2	Failure to treat/provide – SCR
Listing 16.2.6.3	Objective tumor assessments by evaluation – SAF
Listing 16.2.6.4	Detailed tumor assessment – SAF
Listing 16.2.6.5	Time to measurable relapse / Time to Progressive Disease – SAF
16.2.7	Adverse event listings by patient
Listing 16.2.7.1	Adverse events – SAF
Listing 16.2.7.2	Adverse events related to TG4050 – SAF
Listing 16.2.7.3	Serious Adverse events before treatment – SAF
16.2.8	Listing of individual laboratory measurements by patient

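### Protocol 9.4.2 puts efficacy in a set defined by events after first injection; the SAP redefines that set, labels its efficacy outputs SAF and does not record the change

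*Protocol*

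**What the plan says.** **Protocol.** Section 9.4.2 assigns the efficacy endpoints to one set: "The analysis of the efficacy endpoints will be performed on the evaluable population (EPP) for efficacy in each cohort of treated patients". Section 9.1.2 limits that set to patients "without any major protocol deviation who received at least the 6 first weekly injections of TG4050 corresponding to the treatment induction phase", who must also "have at least two baseline and two post-baseline evaluations of CA-125 and one baseline and one post-baseline CT-scan or MRI".

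**SAP, definitions.** Section 6.1 uses the same name for a different set: "all treated patients without any major protocol deviation who received at least 6 injections of TG4050 corresponding to the treatment induction phase". The CA-125, imaging and per-cohort wording is gone. Section 6.2 still builds on it ("The identification of major protocol deviations is critical for the EPP definition"). Section 8.3, on baseline characteristics, still cites it ("Analyses will be based on the SAF / EPP populations"), although 8.3.1 then specifies SAF. The sentence "Given the small number of patients, this population won't be used" in 6.1 comes directly after the entry for the modified EPP.

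**SAP, analyses and outputs.** Section 8.8 describes time to measurable relapse and tumor response without naming an analysis set. Section 7.6.1 promises a number and percentage of complete responders among patients with non-measurable lesions, also without a set. In section 10, Figures 14.2.1-1 and 14.2.1-2 and Listings 16.2.6.1, 16.2.6.3, 16.2.6.4 and 16.2.6.5 (the last titled "Time to measurable relapse / Time to Progressive Disease") are labelled SAF. Listing 16.2.6.2, on failure to treat or provide, is labelled SCR, which suits its content. No output is labelled EPP.

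**The concern.** SAP 7.6.2 and 8.8 start the relapse clock at the first injection, but a patient earns her place in EPP only by what happens afterwards. A set built that way removes patients who do badly early and keeps those who last long enough to qualify. In a single-arm trial no comparator would reveal the effect. These patients need not lack data: protocol 4.3.2 and 6.2.5 keep following anyone who stops treatment for a reason other than progression or death, so EPP would discard results that were collected.

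The second problem is that the documents disagree. Someone writing the report from the protocol would use one EPP. Someone reading SAP 6.1 would find another. Someone working from the output titles would use SAF. With six patients, one person moving in or out changes any percentage visibly.

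**Working it through.** The plan gives no sample size, power or error rate, so there is no figure of its own to reproduce. The check compares text and schedule, followed by an illustration of size.

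**1. The two definitions**

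| Condition | Protocol 9.1.2 | SAP 6.1 |
|---|---|---|
| No major deviation | yes | yes |
| Six injections | yes, the first six weekly doses | yes |
| Two baseline and two post-baseline CA-125 values | yes | no |
| One baseline and one post-baseline scan | yes | no |
| Stated per cohort | yes | no |

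**2. When membership is decided** (nominal days from protocol Appendix II-B; visit windows ignored)
- Weekly dose j falls on Day 1 + 7(j − 1), so dose six falls on Day 1 + 35 = Day 36.
- Post-baseline CA-125 is scheduled on Day 22 and Day 43, so the second value comes at Day 43.
- The first post-baseline scan is scheduled on Day 43.

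**3. Who leaves**
- A patient who stops before dose six for clinical progression, dose-limiting toxicity, death or withdrawal fails both definitions.
- A patient with six doses but no later scan, or no second post-baseline CA-125, fails only the protocol definition.
- A patient with six doses whose progression is first seen on the Day 43 scan meets the injection and scan conditions and is not lost on those grounds.

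**4. Which set each source gives for efficacy**
- Protocol 9.4.2: EPP, by cohort.
- SAP 8.8: none named.
- SAP section 10 titles: SAF.
- SAP 7.6.1 complete-response percentage: none named, and I found no matching table in section 10.

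**5. Size, as an illustration.** Six patients were treated (SAP section 4). The number k of early non-responders that EPP would drop is not in the documents and is assumed. With r responders, the proportion moves from r/6 to r/(6 − k), a multiplication by 6/(6 − k). Intervals are exact Clopper-Pearson 95%, the method in SAP 8.1.

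| r | SAF (n = 6) | k = 1 (n = 5) | k = 2 (n = 4) |
|---|---|---|---|
| 1 | 16.7% (0.4 to 64.1) | 20.0% (0.5 to 71.6) | 25.0% (0.6 to 80.6) |
| 2 | 33.3% (4.3 to 77.7) | 40.0% (5.3 to 85.3) | 50.0% (6.8 to 93.2) |

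The multiplier is 6/5 = 1.2 for k = 1 and 6/4 = 1.5 for k = 2. If each patient independently had probability q of stopping early, the chance of losing at least one of six is 1 − (1 − q)^6. For assumed q of 5%, 10%, 20% and 30% this gives 26.5%, 46.9%, 73.8% and 88.2%. The SAP does not give the split by cohort; within a cohort smaller than six, one exclusion would weigh more.

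**6. A side effect of the SAP version.** SAP 6.2 removes from EPP anyone with a major deviation. Appendix 1 codes measurable disease under RECIST 1.1 as major (EXCL07), whereas SAP 2.1.2 makes measurable disease the entry condition for Cohort B. Read literally, the SAP's EPP would contain no Cohort B patient.

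**The case against.** The strongest reply is that no listed output carries the bias. Every treatment-period efficacy figure and listing in SAP section 10 is SAF, and the document history records under version 3.0 that EPP listings and tables were removed, so the move looks deliberate. No efficacy text in the SAP points to EPP; the mention in 8.3 concerns baseline data. Section 8.2.2 tabulates exclusions and discontinuations with reasons, and six patients listed one by one cannot hide an early failure. The trial is phase I with safety as its primary objective and descriptive statistics throughout.

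All of that stands, and it limits the point to reconciling the documents. It does not remove the point. A history entry shows intent but does not name an efficacy set. Output titles cannot settle the denominator for the percentage in 7.6.1, which has no listed output. The protocol rule still reads as the governing one, because nothing in the SAP says it was set aside. Nor does the sentence "Given the small number of patients, this population won't be used" clearly retire EPP: it is singular and follows the modified EPP.

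**Conclusion.** The point holds as a conflict between protocol and SAP over the efficacy analysis set, of minor to moderate severity. The protocol's rule selects on post-injection events; the SAP's listed outputs do not follow it, and the SAP does not say so. No error rate or power is affected. The 1.2-fold and 1.5-fold multipliers rest on assumed values of k, on the dropped patients being non-responders and on all six patients sharing one denominator. The intervals are so wide that neither set would support a firm efficacy statement.

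Three stronger readings are tempting and not supported:
- A reader might infer that the planned efficacy results are biased. The listed outputs are SAF, so they avoid this selection.
- A reader might infer that every patient who progresses by Day 43 is dropped. Progression first found on that scan, after six doses, does not fail the injection or scan condition.
- A reader might use the protocol's 4.8-month median lead time to estimate how many patients would be lost or how far a median would shift. Protocol 1.2 gives that figure from CA-125 rise to second-line chemotherapy, not from first injection to RECIST relapse or to leaving EPP, and no listed output reports a median time to relapse.

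**What to change.** - In SAP 8.8 and 7.6.1, state that all efficacy results (CA-125, tumor response, time to relapse or progression) use SAF, by cohort, counted from first injection.
- Record this in the SAP as a change from protocol 9.4.2, with the reason.
- Delete EPP from SAP 6.1, 6.2 and 8.3. Alternatively, keep it only as a sensitivity set with one definition and the reason for each exclusion; Appendix 1 would then have to be reconciled with the Cohort B entry condition.

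The cost is SAP wording. No new data are needed, and the listed outputs already carry the SAF label. The one downside is that results may look slightly less favourable than under EPP.

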#### **9.4.3. Translational research**

A statistical analysis plan dedicated to translational research will be provided separately.

